APPENDIX IV

TBI Administration

1.0 **INTRODUCTION**

1.1 **Allogeneic Hematopoietic Cell Transplant**

Allogeneic hematopoietic cell transplantation (HCT) is an effective therapy for a variety of hematologic malignancies and bone marrow failure syndromes. However, it carries a significant risk for treatment-related mortality, primarily due to infection, conditioning regimen-related toxicities, and graft versus host disease (GVHD); which continues to limit its utility. The risk of transplant-related mortality (TRM) is influenced by several factors, including patient age, disease remission status, number of prior chemotherapy regimens, co-morbid diseases, and conditioning regimen intensity. Since the 1980's, several advances have reduced the risk of TRM in patients undergoing allogeneic HCT; including more effective approaches for prevention of infection, enhancements in HLA typing and matching, and GVHD prophylactic regimens [1]. Despite this however, TRM remains high and GVHD remains a major cause of morbidity and mortality amongst allogeneic HCT patients. Even with prophylactic measures, the incidence of acute GVHD is estimated to be 40-50% among patients from HLA identical sibling donors and up to 75% in patients receiving unrelated transplants. Treatment for established GVHD can be difficult, with a mortality rate of 60-80% in patients with grades 3-4 acute GVHD. Approximately 40% of patients with acute GVHD have a durable response to corticosteroid therapy, and there has been little change in this response rate over the past 20 years despite changes to GVHD treatment regimens [2]. Thus the use of improved and effective prophylaxis is of utmost importance.

1.2 **GVHD Prophylaxis**

Currently, GVHD prophylaxis is based on a calcineurin inhibitors (cyclosporine (CsA) or tacrolimus (Tac) also called FK-506) and a short course of methotrexate (MTX). Other options include steroids, mycophenolate mofetil (MMF), and sirolimus. While the combination of Tac and MTX has largely been shown to be superior in the prevention of aGVHD compared to other regimens, toxicities from these regimens are a cause of significant morbidity after allogeneic transplant.

Methotrexate has had a long history of use as a component of GVHD prophylaxis agents in HCT. Initially used as a single agent, it has been shown to be complementary in combination with calcineurin inhibitors cyclosporine and tacrolimus. However, it also may increase the risk of other complications such as mucositis, delayed neutrophil and platelet engraftment and contribute to hepatic and renal toxicities. Mucositis can be severe and debilitating necessitating the need for total parenteral nutrition (TPN) and furthering tissue damage contributing to GVHD. As a result of severe mucositis, doses of MTX must often be held, which may further decrease the efficacy of GVHD prophylaxis.

Tacrolimus is an immunosuppressive macrolide lactone that blocks the earliest steps of T-cell activation by inhibiting the calcium-dependent signal transduction pathway. Although the mechanism of action, pharmacokinetics, and side-effect profile of tacrolimus are similar to those of cyclosporine, its immunosuppressive potency in vitro is 50 to 200 times greater than

that of cyclosporine. Large phase III studies comparing Tac/MTX versus CsA/MTX for both matched related and unrelated donors have been performed and demonstrate superiority of Tac/MTX [3-4].

Mycophenolate mofetil (MMF) has been utilized in an effort to improve GVHD prophylaxis and reduce toxicity. MMF is an ester prodrug of the immunosuppressant mycophenolic acid. Mycophenolic acid inhibits inosine monophosphate dehydrogenase, resulting in the blockade of de novo purine synthesis, thereby limiting proliferation of lymphocytes. MMF is effective in preventing GVHD in animal models, and the combination of a calcineurin inhibitor and MMF is more effective than either agent by itself [5]. The CsA and MMF or Tac and MMF combinations are commonly used as GVHD prophylaxis in patients undergoing reduced intensity transplants. MMF in combination with CsA has been compared to MTX and CsA in 2 small prospective randomized studies for GVHD prophylaxis in patients undergoing myeloablative transplant [6-7]. These studies demonstrated several benefits in the MMF arm, including less severe mucositis, shorter time to neutrophil and platelet engraftment, a reduction in use of TPN and narcotic analgesia, and shorter hospitalization times. The combination of Tac and MMF has been evaluated as GVHD prophylaxis in adults in single-arm phase II trials which have shown the regimen to be well tolerated [8-9].

1.3 Clinical Data to Date

The group at M.D. Anderson Cancer Center has developed a mini-dose methotrexate regimen (5 mg/m² IV on days 1, 3, 6, and 11) in an effort to reduce mucosal and hepatic complications and have published small studies on its use in combination with both CsA and Tac [10-11]. These studies have demonstrated the safety and efficacy of this regimen in HLA matched and 1 antigen mismatched unrelated donors, with an incidence of grade 2-4 acute GVHD of 33-59% and grade 3-4 acute GVHD of 17%. Tac and mini-dose MTX (5mg/m² IV on days 1, 3, and 6 only) has been further tested in combination with a third agent [12-13]. Mizumoto et al used a combination of Tac, mini-dose MTX and MMF as GVHD prophylaxis in reduced-intensity transplants and demonstrated a safe and well tolerated profile with a low incidence of severe grade 3-4 GVHD (5%). While these studies have demonstrated the safety and efficacy of these regimens, there have been no studies directly comparing mini-dose MTX and standard dose MTX based GVHD prophylactic regimens.

2.0 OBJECTIVES

2.1 Primary Objectives

- To determine the incidence, length and severity of mucositis from Day 0 until day of discharge or Day +28 (whichever comes first) after allogeneic bone marrow transplantation comparing Tac, mini-dose MTX and MMF with Tac and MTX.
- To study rates of neutrophil and platelet engraftment comparing Tac, mini-dose MTX and MMF versus Tac and MTX

- To study the incidence of acute graft-versus-host disease in HLA matched related and unrelated allogeneic bone marrow transplantation using a myeloablative preparative regimen comparing Tac, mini-dose MTX and MMF with Tac and MTX.

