2.2 Secondary Objectives

- Length of hospitalization/time to discharge
- Use of TPN (total parenteral nutrition)
- Length of time on continuous infusion narcotics
- Incidence of infection in the first 100 days post-transplantation
- Incidence of hepatotoxicity in first 100 days post-transplantation
- Incidence of nephrotoxicity in first 100 days post-transplantation
- Incidence of pulmonary toxicity in first 180 days post-transplantation
- Incidence and severity of grade II-IV and III-IV acute GVHD
- Incidence and severity of chronic GVHD
- One year relapse-free and overall survival

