11.1.4 Study Parameters Table

Required Assessments	Pre-study (< 42 days prior Allo-HSCT)	During Initial Hospitalization for Allo-HSCT	Post Hospitalization for Allo-HSCT to Study End Point
Tumor characteristics / Site of involvement	X		As clinically indicated
ECOG / Lansky	X		Q visits until 1 year
Bone Marrow Aspirate / Biopsy	X		Day 100 (optional) or as clinically indicated
CBC and diff	X	Daily until ANC >500, plt >20,000, then Q weekly until normal	Q weekly until day 100 and then at follow up visits
Hepatic enzymes (AST, ALT, Alk Phos, Total Bili)	X	Daily until discharge	At follow up visits
Creatinine	X	Daily until discharge	At follow up visits
PT/PTT	X	Q weekly	As clinically indicated
CMV DNA	X	Q weekly	Weekly until D 100, then as clinically indicated
HIV screening	X		
PFT studies (> 6yo)	X		day 100 and as needed
PB chimerism		X (if patient is still in hospital at any time point)	Approximately 1, 2, 3, 6, 9, 12 months or as clinically indicated
HCG (female of childbearing age)	X		
Tac levels		2X / week or as clinically indicated	As clinically indicated
Acute GVHD Monitoring		1X / week starting D +7	Q weekly until day 100
Chronic GVHD monitoring			After D 100, at least every 3 months
Mucositis grading		3X / wk D 0 to D +28 or D/C (which ever occurs first)	
Organ Toxicity assessment		Q weekly	Q visits until 1 year

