11.1.5 Study Assessments

Engraftment

Neutrophil engraftment will be measured by the number of days to reach a neutrophil count of greater than or equal 500/ul for three consecutive laboratory values obtained on different day. The day of engraftment will be the first day of the three consecutive laboratory values

Platelet engraftment will be measured by the number of days to reach a platelet count of greater than or equal 20,000/ul for three consecutive laboratory values obtained on different days independent of platelet transfusions the prior 7 days. The day of engraftment will be the first day of the three consecutive laboratory values.

Acute Graft-Versus-Host Disease

Acute graft-versus-host disease will be monitored daily and will be documented 1X / week from day +7 while patient is hospitalized for transplant. After discharge from hospital, Acute GVHD will be monitored and documented at a minimum of every 21 days till day +100 (or more if clinically indicated). Acute graft-versus-host disease will be graded according to the table shown in Appendix 1. Skin, gastrointestinal, and/or liver biopsies will be obtained, when appropriate, to facilitate the diagnosis. The type and duration of immunosuppressive treatment given for aGVHD will be recorded.

Chronic Graft-Versus-Host Disease

After day 100, patients will be assessed at least every 3 months (+/- 14 days) for cGVHD. cGVHD will be graded as mild, moderate, or severe based on the National Institutes of Health Consensus Development Project according to the table shown in Appendix II. The type and duration of immunosuppressive treatment given for cGVHD will be recorded.

Mucositis

Mucositis will be graded 3 times per week (Mon-Wed-Fri) by the mid-level provider or transplant physician from day 0 until day +28 or day of discharge (whichever occurs first) according to the WHO grading scale shown in Appendix III.

Total Parenteral Nutrition (TPN)

Start and stop dates of TPN will be recorded.

IV Pain Medications

Start and stop dates for the need for continuous IV infusion of narcotics for severe mucositis pain in the form of intravenous infusion or patient controlled analgesia (PCA) will be recorded.

Length of Hospitalization

Length of hospitalization will be measured from date of transplant to date of discharge.

Organ Toxicity

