Information regarding renal, hepatic and pulmonary function will be collected at study entry and will be assessed throughout the time that the patient remains on GVHD prophylaxis. Patients will be assessed at least weekly until day 100 post transplant and then at follow up visits for 1 year post transplant for organ toxicity.

A patient will be considered to have liver dysfunction should the patient have a total bilirubin $\geq 3X$ the upper limit of normal and AST, ALT or alkaline phosphatase $\geq 5X$ the upper limit of normal.

Hepatic veno-occlusive disease will be diagnosed according to criteria set forth by McDonald et al [18]. Patient must have the presence, before day 20 after transplant, of at least two of the following features:

- Bilirubin greater than or equal to 2 mg/dL
- Hepatomegaly and right upper quadrant pain
- Ascites and/or unexplained weight gain greater than 2% from baseline.

A patient will be considered to have renal dysfunction should the patient have a serum creatinine $\geq 3X$ the baseline value, creatinine clearance or GFR $\leq 40\%$ of baseline or dialysis dependence.

A patient will be considered to have pulmonary toxicity based on the following criteria (using CTCAE v4):

- Bronchopulmonary hemorrhage, grade 3 or higher
- Pulmonary edema, grade 3 or higher
- Respiratory failure, grade 4 or higher

Overall Survival and Relapse-Free Survival

Both overall survival and relapse-free survival will be assessed one year from the day of stem cell infusion, T-O or death, which ever is first. One-year-relapse-free and overall survival will be defined by CIBMTR criteria for individual diseases. Suspicion for relapse should be confirmed by bone marrow biopsy and date of biopsy should serve as date of relapse. Biopsy is strongly encouraged but not required if there are compelling medical reasons why biopsy is not feasible or unobtainable or if relapse is otherwise evident and confirmed by peripheral blood flow cytometry.

Evaluation of Chimerism

Donor chimerism will be assessed by analysis of single-tandem repeats on whole marrow and in lymphocyte enriched or sorted CD3+ T cells and CD33+ granulocytes from the blood depending on institution practice. Blood will be obtained for donor chimerism “BME analysis” at approximately 1, 2, 3, 6, 9 and 12 months or as clinically indicated.

Infections

Documented bacterial, viral and fungal infections will be recorded for 1 year after transplantation.

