12.0 MEASUREMENT OF EFFECT

12.1 Incidence, Length and Severity of Mucositis

The incidence, length and severity of mucositis from day 0 to day 28 (or discharge date if earlier) after allogeneic bone marrow transplantation comparing Tac, mini-dose MTX and MMF with Tac and MTX will be determined.

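### Length of mucositis, part of the first primary objective, is observed only until discharge, so if patients go home before healing the arm discharged earlier can appear to have shorter mucositis with no true difference

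*Combined protocol and SAP*

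**What the plan says.** Section 2.1 names the incidence, length and severity of mucositis as the first primary objective, observed "from Day 0 until day of discharge or Day +28 (whichever comes first". Section 12.1 repeats the three components and ends the window at Day 28, "or discharge date if earlier". The mucositis paragraph of Section 11.1.5 has grading on three days a week, "from day 0 until day +28 or day of discharge (whichever occurs first". The Study Parameters Table (11.1.4) says "3X / wk D 0 to D +28 or D/C (which ever occurs first" in the inpatient column and leaves the post-hospitalisation cell for mucositis blank. Section 11.1.3 says that the inpatient assessments continue after discharge, but it refers to that table for the time points, so no usable post-discharge grading is set out.

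Discharge is itself an outcome. Section 2.2 lists "Length of hospitalization/time to discharge" and Section 14.0 compares hospital stay between arms with a Wilcoxon rank sum test. Section 1.2 reports, from two small randomised studies of cyclosporine with MMF against cyclosporine with MTX, less severe mucositis, faster engraftment and shorter hospital stays in the MMF arms. Section 14.0 aims for neutrophil engraftment 4 days earlier, from a mean of 19 days.

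The documents do not define length, name an analysis for it, give discharge criteria, or say how mucositis still present at discharge is recorded.

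**The concern.** The observation period for one primary measure ends at an event that treatment may move. Suppose a patient's mucositis starts on day 5 and heals on day 22, a true length of 17 days. Seen until discharge on day 23, all 17 days are observed. Seen until discharge on day 19, only 19 - 5 = 14 days are observed, although the mucositis is the same. If Group B goes home earlier for other reasons, such as faster engraftment, and some patients still have mucositis when they leave, observed length falls more in Group B than in Group A.

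What is at stake is the reading of the length result. A shorter recorded length in Group B could not then be separated from an earlier discharge. Grades after discharge are not collected, so this could not be repaired reliably at the analysis stage.

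**Working it through.** **1. What the plan sized.** Section 14.0 gives 41% against 16% severe mucositis, one-sided 5%, 80% power, 47 per group. With mean proportion 0.285 and difference 0.25:

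n = [1.645 × √(2 × 0.285 × 0.715) + 0.842 × √(0.41 × 0.59 + 0.16 × 0.84)]² / 0.25² = (1.050 + 0.516)² / 0.0625 ≈ 39.3, so 40 per group.

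The continuity correction gives (39.3/4) × [1 + √(1 + 4/(39.3 × 0.25))]² ≈ 46.9, so 47. The plan's figure is reproduced. It concerns incidence of grade 3-4 mucositis; length has no hypothesis, test or sample size.

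**2. Direction.** If length is counted up to the end of observation,

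observed length = min(resolution day, discharge day, 28) - onset day.

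For a given course of mucositis, an earlier discharge lowers this or leaves it unchanged. With the same true mucositis in both arms, the error favours the arm discharged earlier, or is zero. The Day +28 cap applies to both arms and does not by itself favour either.

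**3. Size, under assumptions.** None of these inputs is in the documents: onset day 5; resolution day gamma-distributed with mean 16, 18, 20 or 22 and SD 5, identical in both arms; discharge day gamma-distributed with mean 23 in Group A and 19 in Group B, SD 5. The 4-day shift borrows the plan's engraftment target and assumes that it carries over to discharge in full.

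| Link between discharge and healing | Spurious shortening in Group B |
|---|---|
| Discharge independent of mucositis | 0.93, 1.31, 1.74, 2.18 days (mean resolution day 16, 18, 20, 22) |
| Leave at most 4 days before healing | 0.5 to 0.9 days |
| Leave at most 2 days before healing | 0.3 to 0.5 days |
| Leave only after healing | 0 |

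The first row implies that 33% to 67% of Group B, and about 16% to 45% of Group A, go home with mucositis.

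**4. Cross-check with a second model.** Assumed: onset about day 6 (SD 2); true mean duration 8, 12 or 16 days (SD half the mean); Group A discharge mean day 22 or 25, SD 5, independent of mucositis; 50 per arm; one-sided 5% Wilcoxon test, which is my choice because the plan names none for length.

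- Equal discharge timing: false-positive rate 4.8% to 5.8%.
- Discharge 2 days earlier in B: spurious shortening 0.13 to 0.91 days, false-positive rate 6% to 25%.
- Discharge 4 days earlier in B: 0.32 to 1.93 days, 11% to 68%. In the central case (discharge day 22 in A, duration 12 days) observed length is 10.4 against 9.1 days and the rate is 43%.
- Central case, 4-day shift, but nobody leaves before healing: 11.7 against 11.7 days, 5.3%.

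**5. Check of the remedy.** Under the step 3 inputs with independent discharge, suppose grading goes on weekly after discharge and length ends at the first grade 0 visit. Healing is then detected later in the arm discharged earlier, and Group B looks about 0.5 days longer with no true difference. Taking the midpoint between the last positive and the first grade 0 assessment, or putting both arms on the same weekly grid, brings the difference to within about 0.1 day.

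**The case against.** The strongest reply is that patients with troublesome mucositis do not go home. Severe mucositis leads to consideration of TPN (6.2.8) and to continuous intravenous narcotics (11.1.5), so independence between discharge and mucositis is the least favourable assumption. This stands, and it is why the 0.9 to 2.2 day range cannot be taken as the estimate. It does not remove the point: the documents contain no rule that mucositis must heal before discharge, Appendix III describes patients with grade 1 or 2 as able to swallow solid food, and length is not limited to grade 3-4.

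Second, the evidence for earlier discharge is indirect. It comes from cyclosporine with MMF, whereas Group B keeps three mini-doses of MTX. The same studies found less severe mucositis alongside the shorter stays, and Section 14.0 does not list a shorter stay among its hopes. This also stands; earlier discharge in Group B is a possibility that the protocol's background raises, not an established fact.

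Third, the in-hospital window is openly stated and no sized conclusion rests on length. That limits the weight of the point, but length is still named in a primary objective.

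A reader might also infer that mucositis present at discharge is recorded as ending that day. The documents do not say so; they give no recording rule. Counting to discharge is one natural reading. Treating such patients as censored at discharge would not be a safe alternative, since that censoring may be informative.

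**Conclusion.** The concern holds as a design weakness of unknown size. Ending observation at discharge lets a treatment-affected event set the window for a primary measure, and any resulting error favours the arm discharged earlier or is zero. With a 4-day discharge shift and identical mucositis, the error runs from zero (discharge only after healing) through 0.3 to 0.9 days (discharge at most 2 to 4 days before healing) to 0.9 to 2.2 days (discharge independent of mucositis). All of these rest on assumed onset, healing and discharge times.

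Two stronger readings are not supported. One is that the plan will certainly show Group B with shorter mucositis: this needs both earlier discharge in B and patients leaving with mucositis, and the documents establish neither. The other is that the main mucositis comparison is compromised: grade 3-4 incidence is affected only if severe mucositis first appears after discharge, and the 47 per group is unchanged. The point should be dealt with before data are collected, but it does not undermine the sized analysis.

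**What to change.** - Make Day +28 the common end of observation for length in both arms, in Sections 2.1, 11.1.4, 11.1.5 and 12.1.
- Record the WHO grade on the day of discharge, then at the weekly post-discharge visits until grade 0 or Day +28. Section 11.1.5 already states, for organ toxicity, "Patients will be assessed at least weekly until day 100 post transplant", and the table has weekly blood counts and CMV testing to day 100. Section 11.1.5 sets post-discharge acute GVHD monitoring at no less than every 21 days while the table says weekly; these should be reconciled so that the visit schedule is clear.
- Define length, including the grade that counts as mucositis, and name its analysis. Treat resolution as interval-censored, or use the midpoint between the last positive and first grade 0 assessment, or compute length in both arms on one weekly grid. Do not end length at the first grade 0 visit under the mixed schedule, since that creates the opposite bias of about 0.5 days.
- Report grade at discharge by arm, so that readers can see how many patients left with mucositis.
- Keep in-hospital grade 3-4 incidence as the sized endpoint.

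The cost is one grade at about one or two existing visits per patient, and less precise resolution dates after discharge. The sample size does not change.

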2.2 Secondary Objectives

- Length of hospitalization/time to discharge
- Use of TPN (total parenteral nutrition)
- Length of time on continuous infusion narcotics
- Incidence of infection in the first 100 days post-transplantation
- Incidence of hepatotoxicity in first 100 days post-transplantation
- Incidence of nephrotoxicity in first 100 days post-transplantation
- Incidence of pulmonary toxicity in first 180 days post-transplantation
- Incidence and severity of grade II-IV and III-IV acute GVHD
- Incidence and severity of chronic GVHD
- One year relapse-free and overall survival

3.0 STUDY DESIGN

3.1 Study Design

This is a prospective randomized trial to determine the effectiveness of different doses of GVHD prophylaxis on mucositis, engraftment and aGVHD. Study consists of two study groups of 50 subjects each.

Group A will receive Tac and MTX (15 mg/m² day +1, 10 mg/m² day +3, +6, +11).

Group B will receive Tac, Mini-dose MTX (5 mg/m² on day +1, +3, +6) and MMF.

